4.2.3 PHASE A EFFICACY ENDPOINTS

1. Characterization of change in OA pain in the target knee as measured by the weekly averages of daily pain numeric rating scale (NRS) from baseline through Week 52 accounting for repeated injections
2. Characterization of change durability of treatment response in OA pain in the target knee as measured by the weekly averages of daily pain NRS through Week 52 elapsed from prior injection to repeat injection
3. Characterization of change in OA function in the target knee as measured by WOMAC physical function subscore (WOMAC Function) from baseline through Week 52 accounting for repeated injections
4. Characterization of change durability of treatment response in OA function in the target knee as measured by WOMAC Function through Week 52 elapsed from prior injection to repeat injection
5. Characterization of change in medial joint space width (mJSW) as measured by radiograph of the target knee from baseline through Week 52 accounting for repeated injections
6. Characterization of change durability of treatment response in mJSW as measured by radiograph of the target knee through Week 52 elapsed from prior injection to repeat injection
7. Characterization of change in OA pain in the target knee as measured by WOMAC pain subscore (WOMAC Pain) from baseline through Week 52 accounting for repeated injections
8. Characterization of change durability of treatment response in OA pain in the target knee as measured by WOMAC Pain through Week 52 elapsed from prior injection to repeat injection
9. Characterization of change in OA disease activity as measured by Patient Global Assessment from baseline through Week 52 accounting for repeated injections
10. Characterization of change durability of treatment response in OA disease activity as measured by Patient Global Assessment through Week 52 elapsed from prior injection to repeat injection

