6.1.5 DOSING AND ADMINISTRATION

SM04690 will be administered in the following dosage strengths:

- SM04690 0.07 mg in 2 mL Injectable Suspension
- SM04690 0 mg; 2 mL placebo (vehicle) injection only

The injectable investigational product or placebo is to be administered by the Unblinded Investigator as a single injection into the target knee joint once each at Day 1 and Week 24 (Phase A), and once each at Week 52 (EOSa) and Week 76 (Phase B). The Week 24, 52 (EOSa), and 76 injections may occur up to two weeks later than the Week 24, 52 (EOSa), and 76 visits, respectively, to allow for resolution of any intercurrent illness (e.g., infection) prior to the injection. The Unblinded Investigator must minimize any contact with the subject following the injections and may not perform any study assessments throughout the duration of the study. All subject contact for the remainder of the study is limited to the Blinded Investigator and other appropriate blinded study personnel.

Only 1 knee will be treated for each subject in this study. The injections can be done either through lateral or medial (including superior/suprapatellar, midpatellar and inferior/anterior) approaches, based on the standard practice of the Unblinded Investigator or the knee examination of the subject. Although not required, the injections may be guided by ultrasound or fluoroscopy without contrast if it is the standard practice of the Investigator.

Only topical anesthetics are allowed prior to study injection. Any local anesthetic injections are prohibited.

Prior to administration of the intra-articular knee injection, the subject should be blinded to observation of the study medication and injection procedure according to the processes specified in the Site-Specific Blinding Plan.

The Unblinded Investigator (injector) should place the needle into the joint and the total volume contained in the syringe is to be injected into the joint space. Because SM04690 drug product is a suspension, prior aspiration of synovial fluid into the syringe containing the injectate should be avoided to prevent trapping of particles within synovial aspirate/cellular content residues. If it is the standard practice of the injector to aspirate a small amount (0.3-0.5 mL) of joint fluid (if present) to confirm correct needle placement, this will have to be done with a separate empty

sterile syringe and, via syringe exchange, subsequently inject study medication using a new syringe.

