Misalignment of both knees will be assessed by the Investigator during the knee examination at Screening Visit 1. In the opinion of the Investigator, subjects with significant and clinically evident misalignment in either knee that would impact subject function must be excluded from the study.

Vital Signs

Vital signs will be measured by a qualified staff member at all visits except Screening Visit 2.

At each time point, the following vital signs will be measured:

- Body temperature
- Pulse rate
- Respiratory rate
- Blood pressure (systolic and diastolic) after the subject rests (sitting or supine) for at least 5 minutes; same resting position should be used for all blood pressure measurements throughout the study

Any measurement that is, in the opinion of the Investigator, abnormal AND clinically significant must be recorded as medical history if found prior to study medication injection or as an AE if found after study medication injection.

Height and Weight

Height measurements will be taken at Screening Visit 1 only. Weight measurements will be taken at Screening Visit 1 and at Weeks 24, 52 (EOSa), 76, and 104 (EOSb) or ET.

Radiograph of Knee Joints

Radiograph of the knee joints will be taken at Screening Visit 1 and at Weeks 24, 52 (EOSa), 76, and 104 (EOSb) or ET.

Detailed instructions for obtaining and managing the radiographs will be provided to the investigational center prior to the initiation of subject enrollment. The intent (as described in the Image Review Charter – Image Acquisition Guidelines) is that radiographs should be obtained in the posterior-anterior (PA) view, whenever possible.

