7.3.3 FOLLOW-UP

Week 4

The Week 4 visit should occur on Day 29 (with a window of + 3 days). Subjects should fast for 8 hours prior to this visit.

The following procedures and assessments will be performed at this visit:

- Collection of AE and concomitant procedures/medication data
- Physical examination, including knee examination of both knees
- Vital signs measurements (pulse rate, blood pressure, respiratory rate, and temperature)

- Venipuncture and collection of samples for clinical laboratory tests and biomarker analysis

Week 12

The Week 12 visit should occur on Day 85 (with a window of \pm 3 days). Subjects should fast for 8 hours prior to this visit.

The following procedures and assessments will be performed at this visit:

- Collection of AE and concomitant procedures/medication data
- Physical examination, including knee examination of both knees
- Vital signs measurements (pulse rate, blood pressure, respiratory rate, and temperature)
- Venipuncture and collection of samples for clinical laboratory tests and biomarker analysis
- qCT of both knees

Week 24

The Week 24 visit should occur on Day 169 (with a window of \pm 3 days). Subjects should fast for 8 hours prior to this visit. Prior to study medication injection, the Investigator should evaluate the subject for suitability to receive the second injection (refer to [Section 6.1.9](#)). The injection may occur up to two weeks later than the Week 24 visit to allow for resolution of any intercurrent illness (e.g., infection) prior to the injection. The subject should complete all other Week 24 assessments and return for an unscheduled visit and injection in the case that they are not able to receive the injection at the Week 24 visit.

The following procedures and assessments will be performed at this visit:

- Collection of AE and concomitant procedures/medication data
- Physical examination, including knee examination of both knees
- Vital signs measurements (pulse rate, blood pressure, respiratory rate, and temperature)
- Weight measurement
- Venipuncture and collection of samples for clinical laboratory tests and biomarker analysis
- Radiograph – bilateral in weight-bearing fixed flexion position, posterior-anterior (PA) view X-ray
- qCT of both knees
- DXA of the spine and hips
- Intra-articular study medication injection (or placebo)

Note: The Week 24 WOMAC and Patient Global Assessment must have already been completed prior to the Week 24 study medication injection.

Week 36

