^b At Day 1, all procedures should be performed prior to study medication injection except for collection of AE and concomitant procedures/medication data.

^c At Week 24, 52 (EOSa), and 76, all procedures should be performed prior to study medication injection.

^d Review medical history to capture End Date(s), if applicable, of any ongoing medical history(ies) collected at screening.

^e Urine pregnancy test on Day 1 will only be performed on female subjects of childbearing potential.

^f Concentrations of bone and cartilage biomarkers are analyzed in the serum.

^g Electronic diary devices will be provided to subjects at Screening Visit 2; subject electronic diary and questionnaire training will be conducted at Screening Visit 2.

^h Electronic diary compliance for daily pain NRS over the screening period will be reviewed at Day 1 prior to randomization to determine subject eligibility.

ⁱ WOMAC questionnaire will be reviewed at Day 1 prior to randomization to determine subject eligibility.

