10. STATISTICAL CONSIDERATIONS

10.1 STATISTICAL AND ANALYTICAL PLANS

This section describes the planned statistical analyses in general terms. A complete description of Phase A statistical analyses will be specified in a statistical analysis plan (SAP). A second SAP will be prepared for Phase B analyses.

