10.4.3 ANALYSIS OF PHASE A EFFICACY AND EXPLORATORY BIOMARKER ENDPOINTS

Changes in the target knee from baseline in Pain NRS, WOMAC Function, WOMAC Pain, mJSW, and Patient Global Assessment will be characterized using MMRM; the models will be evaluated through Week 52. All models will use treatment group, week, treatment×week

interaction, and baseline values as covariates. Unadjusted 95% confidence intervals and P values will be reported.

For WOMAC, mJSW, and Patient Global Assessment, the model will be estimated assuming an unstructured variance-covariance matrix. For Pain NRS, the model will be estimated assuming a Toeplitz variance-covariance matrix. The Toeplitz structure is a more generalized form of autoregressive-1 structure, allowing the data to inform how the correlation between within-subject observations decreases over time instead of implicitly defining a uniform decay structure (Kincaid 2005).

To assess response durability, changes in the target knee from Week 24 (i.e., after second injection) in Pain NRS, WOMAC Function, WOMAC Pain, mJSW, and Patient Global Assessment will be characterized using MMRM; the models will be evaluated through Week 52. All models will use treatment group, week, treatment×week interaction, and Week 24 values as covariates. Unadjusted 95% confidence intervals and P values will be reported.

Baseline-adjusted ANCOVA will be used to analyze the change from baseline in serum bone biomarkers (e.g. PINP and β -CTX) and a serum cartilage biomarker (e.g., COMP) for SM04690 subjects versus placebo. The models will be adjusted for baseline and evaluated at Weeks 4, 12, 24, 36, and 52. Unadjusted 95% confidence intervals and P values will be reported.

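### The Phase A durability model adjusts for the post-randomisation Week 24 value, so its by-week results can show a kept effect as further benefit; the Phase B SAP names no durability contrast and does not say so

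*Protocol*

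**What the plan says.** **Endpoint.** Five of the ten Phase A efficacy endpoints in Protocol 4.2.3 concern durability of response, "through Week 52 elapsed from prior injection to repeat injection".

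**Phase A model.** Protocol 10.4.3 first plans an MMRM of change from baseline through Week 52. It then adds a durability model: "To assess response durability, changes in the target knee from Week 24 (i.e., after second injection) in Pain NRS, WOMAC Function, WOMAC Pain, mJSW". The fifth outcome listed is Patient Global Assessment, and the method is again MMRM through Week 52. Its terms are treatment, week, "interaction, and Week 24 values as covariates". Unadjusted 95% confidence intervals and P values are to be reported.

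**When Week 24 is measured.** Randomisation and the first injection are on Day 1. Protocol 7.3.3 states: "Note: The Week 24 WOMAC and Patient Global Assessment must have already been completed prior to the Week 24 study medication injection". Footnote c of Protocol 7.3.7 extends this: "At Week 24, 52 (EOSa), and 76, all procedures should be performed prior to study medication injection". SAP Appendix 1 sets Week 24 Pain NRS at Days 162 to 168, before the nominal visit on Day 169. For mJSW, "Radiograph of the knee joints will be taken at Screening Visit 1 and at Weeks 24, 52 (EOSa), 76, and 104 (EOSb) or ET", so Week 52 is the only Phase A value after Week 24.

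**Governing document.** Protocol 10.1 defers detail: "A complete description of Phase A statistical analyses will be specified in a statistical analysis plan (SAP"). SAP 5.1 confirms that a separate Phase A SAP was prepared. It is not among the documents reviewed.

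**Phase B.** SAP 3.2.7 keeps five durability endpoints through Week 104, and SAP 5.2 says that Phase B will be analysed much as Phase A was. SAP 12 contains one model, a from-baseline MMRM for Pain NRS, and from-baseline descriptive summaries. SAP 15 lists one change, to the biomarker reference point.

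**The concern.** Durability asks whether the treatment effect holds, fades or grows between injections. The planned model conditions on an outcome that the first injection may already have changed. Nobody is re-randomised at Week 24, so the arms need not be comparable on that value. The resulting by-week estimate is then neither the effect at that week nor the change in effect since Week 24.

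What is at stake is the reading of the results labelled durability. An effect that is merely kept could be reported as continued improvement, with a confidence interval and P value, and a real loss could look smaller than it is. In Phase B, a reader would expect durability results for five endpoints, find no contrast that addresses them, and find no statement that they were left out.

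**Working it through.** **1. Inputs.** The model terms come from Protocol 10.4.3. No interaction of the Week 24 value with week is listed, so one slope serves all weeks. The group size of about 50 per arm comes from Protocol 4.1 and 10.5. The documents give no slope, correlation or effect size for these outcomes, so those below are assumptions. They also give no design figure for durability; the only power figure concerns BMD and does not bear on this point.

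**2. What the coefficient is.** Let D(t) be the arm difference at week t. The model is

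Y(t) − Y(24) = a(t) + τ(t)·treatment + g·Y(24) + error.

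Moving Y(24) to the right gives Y(t) a slope b = 1 + g on Y(24). With complete data the estimate is

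τ(t) = D(t) − b·D(24).

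It equals the effect at week t only if D(24) = 0 or b = 0. It equals the change in effect, D(t) − D(24), only if D(24) = 0 or b = 1. In simulation (50 per arm, seven four-weekly visits, unstructured covariance) the identity held in every data set to rounding error.

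**3. Size, as a share of D(24).** If a share f of the Week 24 effect remains at week t, the model reports f − b. The true change is f − 1, so the difference is 1 − b.

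| Effect at week t | True change | b = 0.5 | b = 0.7 | b = 0.9 |
|---|---|---|---|---|
| Fully kept (f = 1) | 0 | +50% | +30% | +10% |
| Half kept (f = 0.5) | −50% | 0 | −20% | −40% |
| Lost (f = 0) | −100% | −50% | −70% | −90% |

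**4. How often a kept effect looks like a change.** Take D(24) = 0.3 SD and b = 0.7. The offset is 0.3 × 0.3 = 0.09 SD and the standard error is √(2(1 − 0.49)/50) = 0.143 SD, so the interval excludes zero in about 9% of trials. Across D(24) of 0.2 to 0.3 SD and b of 0.7 to 0.9 the figure is 6% to 9%. At D(24) = 0.5 SD it is about 18% for b = 0.7 and 29% for b = 0.5. With D(24) = 0 the model returned the true change.

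**5. What survives.** The offset b·D(24) is the same at every week, so it cancels between weeks: τ(52) − τ(36) = D(52) − D(36). The time course after Week 24 is therefore right for the outcomes with several later visits. For mJSW there is one later visit, the model reduces to a single ANCOVA, and nothing cancels.

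**6. Injection timing.** Two features limit which weeks can serve in a contrast.
- Early visits: Protocol 7.3.3 allows the Week 24 visit from Day 166, although the table in 7.3.7 shows only a later window; the two should be reconciled. Protocol 7.3.4 allows the Week 52 visit from Day 362. The Pain NRS weeks are fixed at Days 162–168 and 358–364, so up to three of the seven days can follow the injection.
- Late injections: Protocol 6.1.5 says that "injections may occur up to two weeks later than the Week 24, 52 (EOSa), and 76 visits". The latest days are 169 + 3 + 14 = 186, 365 + 7 + 14 = 386 and 533 + 7 + 14 = 554, in Weeks 27, 56 and 80. Weeks 36, 64 and 88 lie after these.

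**7. Phase B.** Setting SAP 3.2.7 and 5.2 beside SAP 12 and 15: five durability endpoints are kept, no contrast between injections is named, four outcomes have no model, and the omission is not listed.

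**The case against.** The strongest defence has four parts.

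- **The model is not uninformative.** A reader might infer that it says nothing about durability between injections. That goes too far: week-to-week differences after Week 24 are unaffected by the offset. What stands is that the plan names no such difference and reports by-week results.
- **The first interval is covered.** A reader might also infer that Day 1 to Week 24 is not analysed. The from-baseline MMRM gives valid by-week effects over that period. Only a named durability contrast is missing, and the same holds for Phase B Pain NRS.
- **The Phase A SAP governs.** Protocol 10 describes the analyses in general terms, and the unseen SAP may have refined this model. This limits the Phase A part and leaves the Phase B part untouched.
- **Little is claimed from these results.** Protocol 10.2 plans no formal hypothesis test, and for modest Week 24 effects false signals are rare. The problem is mainly the wrong quantity, and inflated error is secondary.

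It can also be said that SAP 12 states that no estimands are provided for Phase B, and that it drops the from-baseline models for four outcomes generally. That explains part of the reduction but does not tell the reader that durability was dropped. Nor is the complaint that SAP 12 lacks a Week 24-covariate model; it lacks any durability contrast.

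The phrase in 10.4.3 that places Week 24 after the second injection may mean the period studied and not the measurement. As written it conflicts with 7.3.3 and 7.3.7, and the sections should be reconciled.

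**Conclusion.** The concern holds in a limited form. As written in Protocol 10.4.3, the by-week durability results equal D(t) − b·D(24). Read alone, they overstate durability by (1−b) of any Week 24 effect: 50% to 10% of it for assumed slopes of 0.5 to 0.9. The exact result assumes complete data and one common slope; with missing visits it is approximate, and if D(24) = 0 there is no distortion. mJSW is the most exposed outcome, because no later visit lets the offset cancel.

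The documents do not support extending this to the main efficacy results: the from-baseline MMRM is unaffected. They also cannot show what was done in Phase A, since that SAP was not supplied. The Phase B gap, five endpoints with no durability contrast and no declaration, can be confirmed directly from the SAP.

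**What to change.** **Phase A.** Replace the Week 24-covariate by-week results, as the durability measure, with contrasts of treatment effects and 95% confidence intervals from the planned MMRM adjusted only for the Day 1 baseline.
- Lead with contrasts inside each injection interval, such as Week 24 minus Week 12 and Week 52 minus Week 36.
- For Pain NRS, end each interval at the last full week before the earliest allowed injection: Week 23 (Days 155–161) and Week 51 (Days 351–357).
- Give Week 52 minus Week 24 as secondary, stated to span a re-injection. For mJSW it is the only contrast available after Week 24.
- Label all of these supplementary, because the Phase A analysis is complete and the sponsor is unblinded (SAP 4.3, 5.1).

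**Phase B.** In SAP 12, add Week 76 minus Week 64 and Week 104 minus Week 88 to the planned Pain NRS MMRM in the FASB, labelled as added after Phase A unblinding. For WOMAC Pain, WOMAC Function, Patient Global Assessment and mJSW, declare in SAP 15 that durability is descriptive only. If WOMAC and Patient Global Assessment are modelled to Week 104 instead, use a parsimonious covariance such as the Toeplitz form already planned for Pain NRS. An unstructured matrix over 26 monthly visits has 26 × 27/2 = 351 parameters for about 100 randomised subjects.

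**Cost.** No new data are needed, only contrast statements and a declaration. Precision falls somewhat for some contrasts. Under equal correlation between visits, a two-week contrast has √(2/(1+b)) times the standard error of the planned coefficient: 1.20 at b = 0.4, 1.15 at 0.5, 1.08 at 0.7 and 1.03 at 0.9.

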10.4.4 ANALYSIS OF PHASE B ENDPOINTS

Phase B endpoints will be analyzed in a similar fashion as Phase A endpoints. A separate SAP will be prepared for Phase B analyses.

10.4.5 SAFETY ANALYSES

Safety analyses will be performed on subjects who receive a study injection (treatment emergent adverse events). Safety assessments include imaging, physical examinations, vital signs, clinical laboratory tests, collection of AEs, SAEs, and concomitant medications, and general medical evaluations. Safety will be evaluated based on the incidence, seriousness, severity, and relationship of AEs and SAEs, and by changes in clinical laboratory parameters and vital signs, relative to baseline.

10.4.6 BASELINE DESCRIPTIVE STATISTICS

Baseline is defined as the last value recorded for any given parameter prior to study medication injection at Day 1. If a subject never received a study injection, baseline is defined as the last value recorded prior to study termination.

Baseline descriptive statistics will include age, gender, race, height, weight, BMI, and KL Grade

10.4.7 PLANNED INTERIM ANALYSES

This safety study was initially designed as a one-year double-blind study. The protocol was amended to add a built-in, one-year single blind extension (Phase B) after the formal, one-year core study (Phase A) completes. The primary analysis will be after last subject completes Week 52 in Phase A and should not be considered an interim analysis.

10.4.7.1 SAFETY REVIEW

Medical monitoring of study safety assessment data will be performed during periodic safety reviews detailed in the Medical Monitoring Plan.

10.4.7.2 EFFICACY REVIEW

Not applicable to this study.

10.4.8 EXPLORATORY ANALYSES

Refer to [Section 10.4.3](#).

10.4.9 ADDITIONAL SUB-GROUP ANALYSES

Not Applicable.

10.5 SAMPLE SIZE

The sample size for this trial is based upon accepted investigational studies exploring changes in bone density.

Additionally, sample size was also estimated assuming a non-inferiority statistical design. Based upon the subchondral BMD data obtained using qCT in SM04690-01, a coefficient of variation (CV) of 0.30 was presumed to be shared by both treatment and placebo groups; this presumed CV is larger than the observed CVs in SM04690-01. Assuming a Type 1 error of 0.05, SM04690-OA-06 will have 81.6% power to estimate a BMD ratio of 0.93 with a one-sided confidence interval extending to 0.80 with a sample size of 50 subjects per group.

